#### 8.1 CALCULATION OF GFR

The following equations will be used to estimate GFR.

#### Cystatin C Equation

GFR =  $133 \text{ x min (scys/0.8, 1)}^{-0.499} \text{ x max (scys/0.8, 1)}^{-1.328} \text{ x } 0.966^{\text{age}} \text{ x } [0.932 \text{ (if female)}]$ 

## Creatinine-Cystatin C Equation

GFR = 135 x min (scr/k, 1)$$\alpha$$ x max (scr/k, 1) $-0.601$  x min (scys/0.8, 1) $-0.375$  x max (scys/0.8, 1) $-0.711$  x 0.995age x [0.969x (if female)] x [1.08(if black)]

Where, k and  $\alpha$  are defined by gender below, scr = serum creatinine, scys = serum cystatin, min (a, 1) = indicates the minimum of a or 1, max (a, 1) = indicates the maximum of a or 1, and (if *condition*) = 1 if true or 0 if false.

	Female	Male
k	0.7	0.9
α	-0.248	-0.207

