9.5.1.4 Pharmacokinetic, Pharmacodynamic, and Pharmacogenomic/Pharmacogenetic Assessments

PHARMACOKINETIC ASSESSMENTS

Not applicable

PHARMACODYNAMIC ASSESSMENTS

The following will be measured for assessment of CV risk factors:

1. SBP, DBP, heart rate (HR)
2. Triglycerides, total cholesterol, HDL-C, LDL-C
3. FPG, fasting insulin

The following parameters related to renal function will be assessed.

- Urinary ACR

- ACR will be measured in spot urine.
- The following are the definitions of newly developed, worsening, and regression of albuminuria which need to be documented in 2 consecutive scheduled or nonscheduled assessments at least 30 days apart:
 - Newly developed albuminuria, defined as first evidence of microalbuminuria (ACR ≥ 30 $\mu\text{g}/\text{mg}$ in spot urine) **or** macroalbuminuria (ACR ≥ 300 $\mu\text{g}/\text{mg}$),¹¹ and ACR value increases $\geq 30\%$ from previous assessment during treatment
 - Worsening albuminuria, defined as when subjects with microalbuminuria at Baseline develop macroalbuminuria, and ACR value increases $\geq 30\%$ from previous assessment during treatment
 - Regression of albuminuria, defined as when subjects with macroalbuminuria at Baseline develop microalbuminuria or non-albuminuria, or subjects with microalbuminuria at Baseline become non-albuminuric, and ACR value decreases $\geq 30\%$ from previous assessment during treatment

- Estimated glomerular filtration rate (eGFR):
 - eGFR will be calculated by the CKD-EPI equation based on creatinine measurement in the total population and/or cystatin C measurement in a selected population. The full criteria for determining whether creatinine, cystatin C, or an algorithm incorporating both will be used to estimate GFR will be detailed in the statistical analysis plan (SAP).
 - Definitions for newly developed, worsening, and regression of chronic kidney disease (CKD)¹² (see [Appendix 2](#)) in the absence of acute, transient, kidney injury
 - Newly developed CKD, defined as when a subject with eGFR ≥ 90 mL/min per 1.73 body surface area (BSA) and without kidney damage at Baseline changes to CKD Stage 1 or higher classified by the 2002 National Kidney Foundation (NKF) guidelines, where kidney damage referred to in the guideline is defined as the emergence of microalbuminuria as defined above, during treatment

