- b. Assessments are only to be performed if clinically indicated or necessary due to state controlled substance requirements. (revised per Amendment 01)
- c. Window ±10 days for all visits after Visit 2, other than the EOS visit which has a window of +10 days. Month is shown unless otherwise indicated; 1 month = approximately 30 days.
- d. Only for a subset of subjects at selected sites. Baseline echocardiograms will be performed in between Visits 1 and 2, after the results of screening assessments have been obtained but prior to randomization, and subject eligibility is confirmed. ECHOs will be performed until at least 1000 subjects have completed the Month 36 echocardiographic assessment. (revised per Amendment 02)

Table 4 Schedule of Procedures/Assessments in Study APD356-G000-401

Phase	Pre-randomization	Randomization																		
Period	Screening	Treatment																	F/U	
Visit	1	2 ^a	3	4	5	6	7	8	9	10	11	12	13	14	15	16	17	EOT	EOS	Unsch ^b
Month ^c	Days -30 to -1	Day 1	3	6	9	12	15	18	21	24	28	32	36	40	44	48	52	56		
Assessment (revised per Amendment 01)																				

- e. For subjects who discontinue study drug early, these assessments will be stopped after the EOT visit.
- f. Renal function parameters and glycemic profile should be obtained at all specified visits, regardless of study drug status. (revised per Amendment 01)
- g. Serum cystatin C will be measured at Baseline and yearly thereafter in the subpopulation with CKD Stage 1 or 2 at Baseline. Serum creatinine will be measured in chemistry blood samples if chemistry assessments are performed.
- h. Serum pregnancy tests will be conducted at Screening. A urine pregnancy test will be conducted at randomization.
- i. These assessments should be done if a telephone contact is performed in lieu of a clinic visit.

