## **5.1.4** Exploratory Endpoints

- Change from Baseline in CV risk factors at 1 year and yearly thereafter (e.g., body weight, dyslipidemia, insulin level, hypertension, and applicable biomarkers of CV risk and other end-organ diseases). For lipid parameters percent change from baseline will be used
- Change from Baseline in eGFR and ACR at 1 year, yearly thereafter, and at the end of the study. GFR will be estimated using creatinine, cystatin C and a combination of both (Section 8.1).
- Change from Baseline in LFTs (AST, ALT, alkaline phosphatase, GGT, total and direct bilirubin) at 1 year and yearly thereafter
- Proportion of subjects without FDA-defined valvulopathy at Baseline who develop FDA- defined valvulopathy at 2 years and yearly thereafter
- Change from Baseline in estimated pulmonary artery systolic pressure at 2 years and yearly thereafter
- Proportions of subjects with at least a 1-stage reduction in an obesity-related complication (prediabetes, metabolic syndrome, T2DM, hypertension, and hypertriglyceridemia/dyslipidemia) at 1 year and EOS; incidence of other obesity-related complications will be collected through AE reports, medical history, and use of

concomitant medications, based on 2014 Advanced Framework for a New Diagnosis of Obesity as a Chronic Disease (American Association of Clinical Endocrinologists [AACE] and American College of Endocrinology [ACE]). (revised per Amendment 01)

- Change from Baseline in HbA1c, FPG, fasting insulin levels, and homeostatic model assessment insulin resistance (HOMA-IR) at 6 months in the following subpopulations of subjects with T2DM at Baseline: (revised per Amendments 01 and 02)
  - o Subjects with (HbA1c>7%) at Baseline
  - o Subjects who have not been treated with antidiabetic agents at Baseline
  - o Subjects who are on monotherapy with oral antidiabetic agent at Baseline
  - Subjects with early T2DM (duration of diagnosis of diabetes is less than 5 years)
     at Baseline
- Proportion of subjects with reduction in the number of OAD medications or reduction in the dosage of OAD medications at 6 months in the following subpopulations of subjects with T2DM at Baseline: (revised per Amendment 01)
  - o Subjects with (HbA1c > 7%) at Baseline
  - o Subjects who are on monotherapy with oral antidiabetic agent at Baseline
  - Subjects with early T2DM (duration of diagnosis of diabetes is less than 5 years) at Baseline

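### SAP 8.1 omits the creatinine eGFR equation and the marker rule left to it, and the two equations it prints need correction

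*SAP*

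**What the plan says.** Protocol 9.5.1.4 bases eGFR on the CKD-EPI equation, using creatinine in the total population and/or cystatin C in a selected one. It then hands a decision to the SAP: "The full criteria for determining whether creatinine, cystatin C, or an algorithm incorporating both will be used to estimate GFR will be detailed in" that document. Footnote g of Protocol Table 4 fixes who has the second marker: "Serum cystatin C will be measured at Baseline and yearly thereafter in the subpopulation with CKD Stage 1 or 2 at Baseline". Protocol 9.5.1.4 defines Stage 1 or 2 as albuminuria with eGFR above 60.

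SAP 5.1.4, on change in eGFR and ACR, says "GFR will be estimated using creatinine, cystatin C and a combination of both" and refers to Section 8.1. Section 8.1 states which equations "will be used to estimate GFR" and prints two: cystatin C, and creatinine with cystatin C. The combined equation ends with the factors "0.969x (if female)] x [1.08(if black", each in square brackets, and the condition is defined as "1 if true or 0 if false". The cystatin C equation has a sex factor of 0.932 in the same style and no race factor.

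SAP 8.2.1 (Table 4) and 8.2.2 define newly developed, worsening and regressing CKD and an eGFR limb of ESRD (below 15). Neither says which eGFR is meant. SAP 5.4.3 analyses the worsening composite in all subjects, in T2DM and in prediabetes, and renal improvement in T2DM.

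**The concern.** A programmer working from SAP 8.1 has no equation for a subject without cystatin C, although one composite covers all randomized subjects. In the subset that does have cystatin C, three estimates will exist and no rule ranks them.

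The choice is not neutral in a weight-loss trial. The protocol's revision history (Version 4.0) explains that cystatin C was added partly because muscle loss lowers creatinine and can make creatinine-based eGFR inaccurate. If that happens more on active drug, creatinine-based eGFR would look better in that arm for reasons unrelated to the kidney. An event definition that depends on the marker should therefore be fixed in advance.

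The printed formulas also give values that cannot be right, so the section would not survive being coded as it stands.

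**Working it through.** The documents give no worked GFR value, so there is no figure to reproduce. The check has four steps.

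**1. Coverage.** The event definitions set against the cystatin C schedule:

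| eGFR component | Baseline group | Cystatin C scheduled | eGFR from SAP 8.1 alone |
|---|---|---|---|
| Newly developed CKD | eGFR 90 or more, no kidney damage | No | None |
| Worsening to below 90 | 90 or more with albuminuria (Stage 1) | Yes | Cystatin C, combined |
| Worsening to below 60 | 60 to 89, Stage 2 | Yes | Cystatin C, combined |
| Worsening to below 30, or regression to above 60 | 30 to 59 | No | None |

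The eGFR limb of ESRD has the same gap outside the Stage 1 or 2 subset.

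**2. Marker rule.** Protocol 9.5.1.4 defers it to the SAP. SAP 5.1.4 answers for one exploratory endpoint by reporting all three estimates. For the event endpoints, SAP 8.1, 8.2.1 and 8.2.2 are silent.

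**3. Indicator.** Inputs are the printed constants. Take cystatin C = 0.8 and creatinine = k, so that every min and max term equals 1. Age 64 is an illustrative assumption.

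- Read literally, cystatin C equation, man: 133 × 0.966^64 × (0.932 × 0) = 0.
- Read literally, combined equation, non-black woman: 135 × 0.995^64 × (0.969 × 1) × (1.08 × 0) = 0.
- With each factor applied if true and set to 1 otherwise, the combined equation gives 98.0 (non-black man), 98.0 × 0.969 = 94.9 (non-black woman), 105.8 (black man) and 102.5 (black woman). No zeros remain.

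**4. Age base, with indicators corrected.** Non-black man, same marker values:

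- Cystatin C: 0.966^64 = 0.1093, and 133 × 0.1093 = 14.5.
- Combined: 0.995^64 = 0.7256, and 135 × 0.7256 = 98.0.

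| Age | Cystatin C equation | Combined equation |
|---|---|---|
| 40 | 33.3 | 110.5 |
| 50 | 23.6 | 105.1 |
| 64 | 14.5 | 98.0 |
| 75 | 9.9 | 92.7 |

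At cystatin C 0.8 the first equation falls below 15 from age ln(15/133)/ln(0.966) = 63.1. Over cystatin C values of 0.5 to 1.2 at age 64 it gives 18.4 down to 8.5. At age 40, the lowest entry age, it gives only 42.1 even at cystatin C 0.5, yet the subset in which it would be used is defined by eGFR above 60.

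SAP 8.1 also cites reference 5, while the list in SAP 12 ends at 4. Item 4 is the paper on estimating GFR from creatinine and cystatin C.

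**The case against.** The strongest reply is that the documents together supply what SAP 8.1 leaves out. A reader might infer that eGFR cannot be computed for most subjects. That is not supported: the protocol names creatinine CKD-EPI for the total population and cites its source at inclusion criterion 3. Identifying the Stage 1 or 2 subset already requires an eGFR that does not depend on cystatin C. Nor do the documents say what share of subjects falls in that subset.

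A reader might also infer that every man would be analysed with an eGFR of 0. That is not supported either. SAP 8.1 tabulates k and the exponent for men, so a non-zero male value is plainly intended, and no programmer would keep the zeros. A superscript lost in PDF reading is possible, although other superscripts in these equations survived and one factor carries an explicit multiplication sign. The 0.966 could likewise be a misread.

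A third inference, that the sponsor means to choose a marker after unblinding, has no basis. The documents do not plan such a choice; they only fail to rule it out. SAP 9 places derivation rules in separate specifications that may contain the marker rule, but the protocol assigned it to the SAP.

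The impact is bounded. The renal endpoints lie outside the gatekeeping procedure and carry no multiplicity adjustment. Albuminuria, creatinine doubling, dialysis, transplant and renal death need no eGFR. It is also fair to say that making creatinine the main marker sits awkwardly with the muscle-loss concern.

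These points limit the size of the problem. They do not supply the missing rule or reconcile SAP 8.1 with SAP 5.1.4 and the protocol.

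**Conclusion.** The point holds as a specification error in SAP 8.1. The section omits an equation that SAP 5.1.4 relies on it to contain, leaves out the marker rule for the renal events, and prints formulas that fail a simple check. Taken alone, it yields no eGFR event for subjects with Baseline eGFR 30 to 59, and it leaves three unranked estimates in the Stage 1 or 2 subset.

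The zeros are a notation error and not a likely analysis result. The age constants matter more, because they put two estimates for the same man at 14.5 and 98.0, on opposite sides of the ESRD cut. That comparison assumes age 64, cystatin C 0.8 and creatinine equal to k, and that the constants were read correctly from the PDF.

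The reach is the eGFR components of the four secondary renal endpoints and the analyses that classify subjects by eGFR (SAP 5.3.2 and 5.3.4). The main analyses of MACE, MACE+ and T2DM conversion do not use eGFR.

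**What to change.** Amend SAP 8.1 before unblinding at study completion:

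1. Print the creatinine CKD-EPI equation that the protocol cites.
2. State which estimate defines CKD and ESRD events, with the same marker at Baseline and follow-up within a subject. Creatinine is the only marker available in all subjects.
3. Report the cystatin C and combined estimates in the Stage 1 or 2 subset as sensitivity analyses, because muscle loss can lower creatinine.
4. Write each sex and race factor as × c if true, × 1 otherwise.
5. Check the age constant in the cystatin C equation against the source, and correct the reference number.

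The cost is a few lines of text. All inputs are already collected.

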#### 8.2 DETERMINATION OF RENAL IMPAIRMENT OR IMPROVEMENT

### 8.2.1 Determination of new onset or worsening of Renal Impairment

Time from randomization to first occurrence of 2 consecutive assessments within the same component of the composite endpoint or time to first occurrence of renal transplant or renal death, on scheduled or nonscheduled visits at least 30 days apart, indicative of new onset renal impairment or worsening of existing renal impairment (first occurrence of any of the following events: microalbuminuria, macroalbuminuria, worsening albuminuria, newly developed CKD or worsening of CKD, or doubling of serum creatinine, or any of the following: ESRD, renal transplant, renal death). Table 4 presents the definitions for each of these events and Appendix 13.2 presents the definition of Chronic Kidney Disease (CKD) stages.

Table 4 Definitions of new	1 1 1	• •	1
Lobio / Hotinitions of nov	IN CONDON OF	WARRANINA AT RANG	I impoirment avents
Table 4 Delillions of new	iv develon or	WOLSEILING OF LEUX	i illiliali illelli evellis
THE I Delimitions of her	i, action or	" or seming or rema	

Renal Impairment Event	Definition
Newly Developed Albuminuria	For subjects without any microalbuminuria (ACR ≥ 30 μg/mg in spot urine), or macroalbuminuria(ACR ≥ 300 μg/mg in spot urine) at baseline or subject shows first evidence of;  • microalbuminuria (ACR ≥ 30 μg/mg in spot urine) with an ACR value increased ≥ 30% from Baseline  or  • macroalbuminuria(ACR ≥ 300 μg/mg in spot urine) with an ACR value increased ≥ 30% from Baseline
Worsening albuminuria	microalbuminuria present at Baseline and develops macroalbuminuria, and ACR value increases ≥30% from baseline assessment during treatment
Newly develop CKD	eGFR ≥ 90 mL/min per 1.73 body surface area (BSA) and without kidney damage at Baseline changes to CKD Stage 1 or higher classified by the 2002 National Kidney Foundation (NKF) guidelines, where kidney damage referred to in the guideline is defined as the emergence of microalbuminuria as defined above, during treatment
Worsening of CKD	CKD Stage 1 or higher defined by NKF guidelines worsens to higher CKD stages (eGFR ≥ 90 with albuminuria at Baseline decreases to < 90, or eGFR 60 to 89 at Baseline becomes <60, or eGFR 30 to 59 at Baseline becomes < 30 mL/min per 1.73 BSA) during treatment
Doubling of serum creatinine	creatinine value is at least 2 times the Baseline value and ≥ 1.5mg/dL during treatment
ESRD	eGFR < 15 mL/min per 1.73 body surface area (BSA) or renal dialysis (captured as an SAE)
renal transplant	Captured as an SAE
renal death	Adjudicated death event by SAE

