8.2 SECONDARY OBJECTIVES

Key Secondary Objective

- To confirm that, in subjects with prediabetes at Baseline based on the 2013 ADA guideline, lorcaserin HCl 10 mg BID reduces the incidence of conversion to T2DM compared to placebo (revised per Amendments 01 and 02)

Other Secondary Objectives (revised per Amendment 02)

MACE and MACE+ Related: (revised per Amendment 02)

- To determine whether the rates of the individual events comprising the MACE+ endpoints are different in subjects on lorcaserin compared to those on placebo
- To determine whether lorcaserin reduces all-cause mortality compared with placebo

Diabetes and Prediabetes Related: (revised per Amendment 02)

- To evaluate the effect of lorcaserin HCl 10 mg BID compared to placebo on conversion to normal glucose homeostasis at 1 year and yearly thereafter in subjects with prediabetes at Baseline (revised per Amendment 01)
- To evaluate whether in all subjects without any type of diabetes at Baseline, lorcaserin HCl 10 mg BID reduces the incidence of conversion to T2DM compared to placebo (revised per Amendment 01)
- To confirm that, in subjects with T2DM at Baseline, lorcaserin HCl 10 mg BID improves glycemic control (HbA_{1c}) compared to placebo at 6 months

Renal Related: (revised per Amendment 02)

- To evaluate the long-term effect of lorcaserin HCl compared to placebo on renal function in all subjects (revised per Amendment 01)
- To evaluate the long-term effect of lorcaserin HCl compared to placebo on renal function in subjects with T2DM at Baseline
- To evaluate the long-term effect of lorcaserin HCl compared to placebo on renal function in subjects with prediabetes at Baseline (revised per Amendment 02)

Safety Objectives (revised per Amendment 02)

- To evaluate echocardiographically determined cardiac valvular function and pulmonary arterial pressure changes associated with treatment with lorcaserin HCl 10 mg BID compared to placebo at 1 year
- To evaluate the long-term safety of lorcaserin HCl 10 mg BID

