 - Worsening of CKD, defined as when a subject with CKD Stage 1 or higher defined by NKF guidelines worsens to higher CKD stages (eGFR ≥ 90 with albuminuria at Baseline decreases to < 90 , or eGFR 60 to 89 at Baseline becomes < 60 , or eGFR 30 to 59 at Baseline becomes < 30 mL/min per 1.73 BSA) during treatment
 - Regression of CKD, defined as when a subject with CKD Stage 1 or higher at Baseline improves to normal or lower stages by NKF guideline (eGFR ≥ 90 with albuminuria at Baseline improves to eGFR ≥ 90 without albuminuria, or eGFR 60 to 89 at Baseline becomes eGFR ≥ 90 with or without albuminuria, or eGFR between 30 to 59 at Baseline improves to > 60 mL/min per 1.73 BSA) during treatment
- Serum creatinine:
 - Doubling of serum creatinine concentration, defined as when a subject's creatinine value is at least 2 times the Baseline value and ≥ 1.5 mg/dL during treatment
- Serum cystatin C:
 - Serum cystatin C will be measured to estimate eGFR in the population of subjects who are in CKD Stage 1 or 2 at Baseline. CKD Stage 1 or 2 is defined as albuminuria and eGFR > 60 mL/min per 1.73 BSA

Additional diabetes-related microvascular complications will be assessed by monitoring AEs associated with retinopathy and neuropathy . (revised per Amendment 01)

The following parameters related to NAFLD will be measured: aspartate aminotransferase (AST), alanine aminotransferase (ALT), alkaline phosphatase, gamma glutamyl transpeptidase (GGT), total and direct bilirubin

Obesity-related complications that are not assessed by any of the objective measures listed in this protocol may be evaluated using data from AE reporting, changes in concomitant medications, or reports of changes in medical history. (revised per Amendment 01)

BIOMARKER ASSESSMENTS

The following inflammatory biomarkers will be assessed to further define the CV risk study population and to investigate potential correlation with changes in CV risk factors, MACE, and MACE+, as well as weight loss and susceptibility to diabetes:

- hsCRP will be measured at the time of Screening and will be followed up yearly through EOT.
- Fibrinogen will be measured at the time of randomization and will be followed up yearly through EOT.
- For subjects who provide consent, other biomarkers related to obesity, diabetes, CV disease, and associated risk factors will be evaluated in serum and plasma samples in selected countries, where applicable (see [Appendix 5](#)).

PHARMA GENOMIC ASSESSMENTS

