Appendix 2 Classification of Chronic Kidney Disease

Chronic Kidney Disease: A Clinical Action Plan			
Stage	Description	GFR (mL/min/1.73m²)	Action*
	At increased risk	≥ 90 (with CKD risk factors)	Screening CKD risk reduction
1.	Kidney damage with normal or ↑ GFR	≥90	Diagnosis and treatment Treatment of comorbid conditions, slowing progression, CVD risk reduction
2.	Kidney damage with mild ↓ GFR	60-89	Estimating progression
3.	Moderate ↓ GFR	30-59	Evaluating and treating complications
4.	Severe ↓ GFR	15-29	Preparation for kidney replacement therapy
5.	Kidney Failure	<15 (or dialysis)	Replacement (if uremia present)

Shaded area identifies patients who have chronic kidney disease; unshaded area designates individuals who are at increased risk for developing chronic kidney disease. Chronic kidney disease is defined as either kidney damage or GFR <60 mL/min/1.73 m² for ≥3 months. Kidney damage is defined as pathologic abnormalities or markers of damage, including abnormalities in blood or urine tests or imaging studies.
* Includes actions from preceding stages.
Abbreviations: GFR, glomerular filtration rate; CKD, chronic kidney disease; CVD, cardiovascular disease.

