### 13.2 Classification of Chronic Kidney Disease

Stage	Description	GFR (mL/min/1.73m 2 )	Action*
	At increased risk	≥90 (with CKD risk factors)	Screening CKD risk reduction
1	Kidney damage with normal or GFR	≥90	Diagnosis and treatment: Treatment of comorbid conditions, slowing progression, CVD risk reduction
2	Kidney damage with mild GFR	60-89	Estimating progression
3	Moderate GFR	30-59	Evaluating and treating complication
4	Severe GFR	15-29	Preparation for kidney replacement therapy
5	Kidney Failure	<15 (or dialysis)	Replacement (if uremia present)

Shaded area identifies patients who have chronic kidney disease; unshaded area designates individuals who are at increased risk for developing chronic kidney disease. Chronic kidney disease is defined as either kidney damage or GFR <60 mL/min/1.73 m2 for 3 months. Kidney damage is defined as pathologic abnormalities or markers of damage, including abnormalities in blood or urine tests or imaging studies.

Abbreviations: GFR, glomerular filtration rate; CKD, chronic kidney disease; CVD, cardiovascular disease.

\* Includes actions from preceding stages.

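### The CKD definitions in SAP Table 4 and the protocol contradict themselves on whether a subject with baseline eGFR 60 to 89 and no albuminuria has an event on falling below 60

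*SAP*

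**What the plan says.** One renal objective in Protocol 8.2 is "To evaluate the long-term effect of lorcaserin HCl compared to placebo on renal function in all subjects". It is served by a time-to-first-event composite, which is also analysed in the T2DM and prediabetes sets. SAP 8.2.1, Table 4, defines the components and refers to Appendix 13.2 for the CKD stages. The synopsis and section 9.5.1.4 of the protocol carry the same CKD definitions.

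- Newly developed CKD: "eGFR ≥ 90 mL/min per 1.73 body surface area (BSA) and without kidney damage at Baseline changes to CKD Stage 1 or higher".
- Worsening of CKD, opening clause: "CKD Stage 1 or higher defined by NKF guidelines worsens to higher CKD stages".
- Worsening of CKD, bracket: three limbs. The first is "eGFR ≥ 90 with albuminuria at Baseline decreases to < 90", the second is "or eGFR 60 to 89 at Baseline becomes <60", and the third is a fall from 30–59 to below 30.

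On staging, Protocol Appendix 2 and SAP Appendix 13.2 agree: "Chronic kidney disease is defined as either kidney damage or GFR" below 60. Stage 2 in SAP 13.2 is "Kidney damage with mild GFR" (a reduction symbol appears to be lost from the extracted text). The cystatin C paragraph of Protocol 9.5.1.4 adds "CKD Stage 1 or 2 is defined as albuminuria and" an eGFR above 60.

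**The concern.** Take a subject with baseline eGFR 75 and ACR below 30 µg/mg. The newly developed CKD row excludes this subject because baseline eGFR is not at least 90. The opening clause of the worsening row excludes the subject because no CKD is present at Baseline. The bracket in that same row includes the subject. Two programmers working faithfully from Table 4 could therefore assign different event status to the same data.

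One of the two outcomes is also hard to defend. A confirmed fall from 95 to 55 without albuminuria would be an event, and a confirmed fall from 75 to 55 would not, although both subjects end in Stage 3 under the plan's own appendix.

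**Working it through.** The plan states no event count or power for the renal composite, so there is no figure to reproduce. The check is a reading of the definitions followed by a look at the other components.

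**1. Does this subject have CKD at Baseline?** The appendices require kidney damage or GFR below 60. Without albuminuria, the plan's marker of kidney damage, and with eGFR 60 to 89, neither condition is met. The subject is in no CKD stage.

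**2. Event status by reading.** The last column applies the rule proposed under the fix. Falls are taken as confirmed on two consecutive assessments.

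| Baseline eGFR, albuminuria | Follow-up eGFR | Opening clause governs | Bracket governs | Proposed rule |
|---|---|---|---|---|
| 95, no | 55 | newly developed | newly developed | newly developed |
| 95, yes | 55 | worsening | worsening | worsening |
| 75, yes | 55 | worsening | worsening | worsening |
| 75, no | 55 or 28 | **none** | **worsening** | newly developed |
| 50, no | 28 | worsening | worsening | worsening |

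Only the 75-without-albuminuria profile depends on the reading.

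**3. Would another component catch the fall?** Creatinine doubling requires at least twice the baseline value and at least 1.5 mg/dL. ESRD requires eGFR below 15 or dialysis. Take eGFR as proportional to creatinine^(−e). The supplied text of SAP 8.1 shows only the cystatin C and combined equations, and cystatin C is scheduled only for subjects with CKD Stage 1 or 2 at Baseline. I therefore assume e = 1.0 to 1.3 for a creatinine-only estimate.

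- Creatinine rise for 75 to 55: (75/55)^(1/e) = 1.36 at e = 1.0 and 1.27 at e = 1.3, a rise of 27–36%.
- Creatinine rise for 89 to 59.9: (89/59.9)^(1/e) = 1.49 and 1.36, a rise of 36–49%.
- eGFR at doubling, starting from 75: 75 × 2^(−e) = 37.5 and 30.5.

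Even with the combined equation's creatinine exponent of 0.601, the fall from 75 to 55 needs a 1.68-fold rise, still short of doubling. Doubling and ESRD therefore do not generally register the crossing of 60. New albuminuria, transplant and renal death remain possible events, but they are different events.

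**The case against.** The best defence is that the bracket is the operative definition. It prints the 60–89 transition, and its first limb states albuminuria while its second does not, which may be deliberate. The baseline tables (Protocol 9.7.1.4, SAP 5.2.4) list GFR bands separately from albuminuria, which could suggest staging by band. The protocol sentence tying Stage 1 or 2 to albuminuria sits in the paragraph that selects subjects for cystatin C, not in the endpoint definition. SAP 9 places derivation rules in separate documents, which might settle the matter.

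Much of this stands. A reader might infer that the composite has no event at all for these subjects; the documents do not support that, because the bracket names the transition.

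The defence does not remove the contradiction, however. The staging does not rest on the cystatin C paragraph alone: Appendix 13.2, to which SAP 8.2.1 itself refers, requires kidney damage for Stage 2, and the baseline table labels the 60–89 band as kidney damage too. Reading the bracket alone also means calling a first entry into CKD a worsening of CKD. A programming document may record a choice, but Table 4 does not make one.

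The consequence is also limited. These endpoints are outside the gatekeeping procedure and carry no type I error adjustment (SAP 5.3.3 and 5.4.3). The rule is the same in both arms, so no direction of bias is shown. Affected subjects can still have albuminuria or late-stage events, and they enter the exploratory ITT model of eGFR change (SAP 5.8).

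**Conclusion.** The point holds as an internal contradiction. One baseline profile, eGFR 60 to 89 with ACR below 30 µg/mg, has two defensible event statuses in all three renal-impairment secondary endpoints. The textual conclusion needs no numerical assumption; only the check on creatinine doubling does (e = 1.0 to 1.3).

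The size in events cannot be derived, because neither document gives baseline eGFR by ACR or a rate of confirmed falls below 60. A count built on assumed shares and rates would also be zero if the bracket governs. If the opening clause governs, it would overstate the loss, because subjects with an earlier albuminuria event are already counted.

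Two further inferences should be resisted. That this is the commonest route into Stage 3 has no support in the documents. Nor is it shown that the composite becomes mainly an albuminuria endpoint: several eGFR transitions count under either reading.

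**What to change.** Before unblinding, state in SAP Table 4 and in the protocol definition that a confirmed fall to eGFR below 60 counts for every subject with baseline eGFR of at least 60:

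- as newly developed CKD if there is no albuminuria at Baseline, by extending that row to baseline 60–89;
- as worsening of CKD if there is albuminuria at Baseline, by adding that condition to the 60–89 limb.

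Make the two edits together. Adding the albuminuria condition alone would resolve the contradiction by dropping the event. If the sponsor always meant the bracket to govern, the composite is unchanged for these falls and only the component label moves.

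Reconcile the regression of CKD definition (Protocol 9.5.1.4, SAP 8.2.2) as well. It opens by requiring CKD Stage 1 or higher at Baseline, then lists a rise from 60–89 to at least 90 without requiring albuminuria at Baseline.

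The cost is a short SAP revision, documented as Protocol 9.7.5 requires, and a protocol change under section 11.1. No new data are needed: creatinine and ACR are already scheduled regardless of study drug status (Protocol Table 4, footnote f). The downside is that some falls that only just cross 60 will count, as they already do for profiles covered by the existing rule.
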